5.2.3 Severity

The severity of the event/reaction will be assessed according to the following terms and assessments. The intensity of an event should not be confused with the term “serious” which is a regulatory definition based on patient/event outcome criteria.

Mild: Some discomfort noted but without disruption of daily life

Moderate: Discomfort enough to affect/reduce normal activity

Severe: Complete inability to perform daily activities and lead a normal life

5.3 Notification and reporting Adverse Events or Reactions

Data on ARs, SARs and SAEs will be collected. If the AR is **not** defined as SERIOUS, the AR will be recorded in the CRF and the participant will be followed up by the research team. All ARs will be documented in the CRF.

5.4 Notification and Reporting of Serious Adverse Events/Reactions

All SAEs including SARs will be recorded in the subjects’ notes, the CRF, the sponsor SAE form and reported to the co-ordinating site. **Related and unexpected SAE’s should be reported to the sponsor at [contact] or by fax on: [name])** within 24 hours of PI or co-investigators becoming aware of the event. Nominated co-investigators can be authorised to sign the SAE forms in the absence of the CI at the co-ordinating site or the PI at the participating sites. The original and any subsequent follow up of SAE Forms together with the fax confirmation sheet must be kept with the investigator site file at the study site.

Additionally related and unexpected SAE’s will be reported to the Ethics committee within 15 days.

6 Statistical Considerations

6.1 Primary Endpoint

CO validated sustained abstinence rates at 52 weeks post-TQD

6.2 Secondary Endpoints

- CO validated sustained abstinence rates at 4 and 24 weeks post-TQD
- CO validated sustained abstinence rates between 24 and 52 weeks
- 7-day point prevalence abstinence at 4, 24 and 52 weeks
- Smoking reduction in participants who did not achieve full abstinence
- Treatment ratings (e.g. satisfaction, helpfulness)

- Changes in urges to smoke and other tobacco withdrawal symptoms at 1 and 4 weeks.
- Adverse reactions
- Cost-efficacy of the interventions.

Abstinence at 4 weeks after TQD would be defined as a self-report of no smoking of conventional cigarettes (not a puff) for the previous 2 weeks, validated by a CO reading of <8ppm. Participants who do not provide a CO reading at Week 4 will be considered to be smoking. 24 and 52 week sustained abstinence will be calculated in accordance with the Russell Standard [50] as a self-report of smoking no more than 5 cigarettes since 2 weeks post-TQD. This self-report will be validated by CO readings as above for the 52 week follow-up. Participants lost to follow-up or not providing biochemical validation will be included as non-abstainers.

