4.4 Schedule of Treatment for each visit

Identical multi-session behavioural support will be provided to both groups. The exact procedures differ slightly between the different study sites, but usual care for smoking cessation involves face-to-face support sessions (Withdrawal Oriented Treatment [46]), which usually begin 1-2 weeks prior to the TQD. Clients attend weekly for several weeks after the TQD. Study data will be collected face-to-face at the first (baseline) session, the TQD, and for the first 4 weeks post-TQD.

Participants would also be contacted by telephone at 24 and 52 weeks post TQD to obtain smoking status and assess EC/NRT/other product use and adverse reactions; those who report abstinence or a reduction in smoking by at least 50% would be asked to provide a CO reading at 52 weeks.

Participants would be compensated £20 for their travel and time at the 52-week visit.

Control Group

Participants will be informed about the range of NRT products available at the baseline session. The supply of NRT differs slightly between the different study sites. For example, the Tower Hamlets SSS provides NRT via a letter of recommendation (LOR) to supply on a fortnightly basis for the first 4 weeks, which clients take to a pharmacist to exchange for NRT paying a prescription charge of £8.05, if applicable (some 50% of SSS clients are normally exempt from the charge) whereas East Sussex SSS provide NRT by direct supply at no charge. For those sites giving LORs, participants will be given an LOR at their baseline session (as per standard practice) and instructed to collect the NRT and bring it to their TQD session. At the TQD those randomised to the NRT condition will keep their NRT and have their first use during the session. For sites that provide NRT on direct supply, participants randomised to the NRT condition will be provided with their NRT during the TQD session. For all sites, detailed instructions on use and information on common side effects will be provided as part of the behavioural support. At the completion of the study treatment period participants can request further supplies of NRT in line with the SSS standard practice (for example, at the Tower Hamlets service, patients can request further 2 week LOR supplies of NRT up to a total of 12 weeks).

Intervention Group

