4.8 Schedule of Assessment

Measures/ Procedures	Study session							
	Baseline	TQD	TQD+1 week	TQD+2 weeks	TQD+3 weeks	TQD+4 weeks	TQD+24 weeks	TQD+52 weeks
Informed consent	X							
Baseline questionnaire	X							
Current illness	X		X	X	X	X	X	X
Current medication	X		X	X	X	X	X	X
Randomisation		X						
Commitment form		X						
CO validation	X	X	X	X	X	X		X (if report abstinence or at least 50% reduction)
MPSS	X	X	X			X		
Smoking status/CPD	X	X	X	X	X	X	X	X
Adverse reactions			X	X	X	X	X	X
EC/NRT ratings			X			X		
Quantity/dose of EC/NRT used and helpfulness		X	X	X	X	X	X	X
EC dispensed, demonstration on first use		X		X				
NRT* dispensed, demonstration on first use		X		X		X		
EQ5D questionnaire	X						X	X
Smoking cessation service and health service use	X						X	X

* Dispensing sessions may differ slightly between sites depending on local SSS practices

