6.4 Statistical Analysis

Analyses will be undertaken after the last participant has completed the 12-month follow-up and the database has been locked.

For the primary analysis the proportion of people remaining abstinent at a year will be compared between the study arms using Chi-squared test with a secondary logistic regression adjusted for study site, sex, age, education, marital status, occupation, entitlement to free prescriptions, ethnicity, daily cigarette consumption, FTCD, age started smoking, partner smoking status, previous smoking cessation medicines used.

For the secondary analyses, we will examine the differences between study arms in the proportions of participants with sustained abstinence at 4, 24 and 52 week follow-up, and sustaining a 50% or greater reduction in baseline cigarette consumption and CO levels at 52 weeks, using Chi-squared test/logistic regression. The frequency of

adverse reactions will also be compared between arms. Between-group differences in urges to smoke and other tobacco withdrawal symptoms will be examined using ANOVA, controlling for baseline ratings. We will also examine time to relapse in a secondary analysis using a Cox analysis with model adequacy assessed by cumulative martingale residuals. An intention to treat analysis will be used with participants lost to follow-up or not providing biochemical validation included as non-abstainers [50]. A sensitivity analysis will be conducted with only participants who attended at least one treatment session from the TQD included.

Economic analyses

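### The 24-week sustained abstinence endpoint is labelled CO-validated although no CO reading is taken at 24 weeks, and the missing-validation rule has no time limit

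*Protocol*

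**What the plan says.** The protocol describes the 24-week outcome in several places, and they do not agree.

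- **Endpoint list (section 6.2).** The first secondary endpoint is "CO validated sustained abstinence rates at 4 and 24 weeks post-TQD". A separate item lists 7-day point prevalence at 4, 24 and 52 weeks, with no mention of CO.
- **Contact (section 4.4).** "Participants would also be contacted by telephone at 24 and 52 weeks post TQD to obtain smoking status". People who report abstinence, or at least a halving of their smoking, "would be asked to provide a CO reading at 52 weeks". No reading is requested at 24 weeks.
- **Schedule (section 4.8).** The CO row is marked at baseline, TQD and weeks 1 to 4. It is blank at TQD+24 weeks, and the 52-week cell reads "X (if report abstinence or at least 50% reduction".
- **Definition (section 6.2).** Week 4 has its own CO criterion and its own sentence on missing readings. Sustained abstinence at 24 and 52 weeks is then defined "as a self-report of smoking no more than 5 cigarettes since 2 weeks post-TQD", followed by: "This self-report will be validated by CO readings as above for the 52 week follow-up".
- **Missing-validation rule.** Section 6.2 continues: "Participants lost to follow-up or not providing biochemical validation will be included as non-abstainers". Section 6.4 repeats it for the intention-to-treat analysis, with "participants lost to follow-up or not providing biochemical validation included as non-abstainers", after listing the 4-, 24- and 52-week comparisons. The synopsis has it too. None of the three gives a time point.
- **Objectives (synopsis and section 2.1).** Abstinence at 4 weeks and 6 months is listed without reference to CO.

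**The concern.** There are two linked problems. First, the endpoint list promises a measurement that the schedule does not collect. An analysis plan can define a derivation, but it cannot supply readings that were never taken.

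Second, the rule on missing validation is written without limit. It follows directly on the definition of 24- and 52-week abstinence, and in section 6.4 it follows a list that includes 24 weeks. An analyst who programs it as written would count everyone as a non-abstainer at 24 weeks. An analyst who sets it aside would be reporting self-report, under a label that says CO-validated, beside 4- and 52-week rates that really are validated. Participants know which product they were given (section 4.4 has them sign a commitment to it), so unverified self-report is a weaker measure here, and readers should be told when they are looking at it.

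The text leaves room for more than one derivation, and the results differ widely. The derivation should be settled in writing before the data are seen.

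**Working it through.** **Is there a plan figure to reproduce?** Not for 24 weeks: the protocol gives no rate, sample size or power for that endpoint. The nearest figure is the total of 886 (443 per arm) in section 6.3, which concerns the 12-month rate. It reproduces to within 3% with a two-sided 5% continuity-corrected comparison of proportions: 864 for 14% against 23.8% (14% × 1.7) at power 0.95, and 874 for 14% against 21% at power 0.75. It is used below only for the arm size.

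**Where is CO available for each abstinence endpoint?**

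| Endpoint (section 6.2) | Labelled CO-validated? | CO scheduled (section 4.8)? | Consistent? |
|---|---|---|---|
| Sustained, 4 weeks | yes | yes, week 4 | yes |
| Sustained, 24 weeks | yes | no | **no** |
| Sustained, 52 weeks (primary, section 6.1) | yes | yes, week 52 if abstinence or reduction is reported | yes |
| Sustained, 24 to 52 weeks | yes | yes, the week-52 reading | yes |
| Point prevalence, 24 weeks | no | no | label yes; reached by the unlimited rule |

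Only one label is wrong. The unlimited rule touches that endpoint and 24-week point prevalence.

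**What would each derivation give at 24 weeks?** Inputs from section 6.3: 12-month rates of 14% (usual care) and 21% or 24% (EC), and 25% relapse between 6 and 12 months. The protocol applies the 25% to an EC cohort. Applying it backwards to both arms is an assumption made here for illustration only.

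1. *Rule read literally.* CO readings scheduled at 24 weeks: 0. Abstainers: 0/443 and 0/443. The abstinent column of the 2×2 table is empty, with expected counts 443 × 0/886 = 0, so neither the chi-squared test nor the logistic regression can be carried out.
2. *Self-report, with loss to follow-up counted as smoking.* 24-week rate = 12-month rate / (1 − 0.25).
   - Usual care: 0.14/0.75 = 18.7%, about 83/443.
   - EC: 0.21/0.75 = 28%, about 124/443; or 0.24/0.75 = 32%, about 142/443.
3. *24-week status confirmed by the 52-week CO.* The protocol does not state this, but an analyst might try it to rescue the label. Anyone abstinent at 24 weeks who relapsed later would fail, so about a quarter of the 24-week abstainers would drop out. The counts would fall back to the 52-week ones: 443 × 0.14 = 62, and 443 × 0.21 = 93 or 443 × 0.24 = 106.

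On these illustrative figures the usual-care count is 0, 83 or 62 depending on the derivation, and the EC count is 0, 124 to 142, or 93 to 106.

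**Which derivation does the text favour?** The second. In section 6.2 the sentence just before the rule ties CO validation of the 24/52-week self-report to the 52-week follow-up. Section 4.4 asks nobody for a reading at 24 weeks, so failing to provide validation most naturally describes people who were asked and did not comply.

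**The case against.** The strongest reply is that this is a labelling slip in one line. The mode of contact, the schedule and the operational definition all point to self-report at 24 weeks, and the objectives in the synopsis and section 2.1 mention no CO for 6 months. On that view the endpoint has a usable definition and only its name is wrong. The statistical analysis plan, which is not at hand, may also set out the derivation.

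Much of this stands. A reader might infer that the protocol scores every participant as smoking at 24 weeks. The documents do not support that as a flat statement: it follows only if the rule is detached from the sentence before it. A reader might also infer that two endpoints are mislabelled. Only the sustained one is, because 24-week point prevalence carries no CO label.

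Two things survive the reply. The silence of the objectives is weak evidence, because the same objective covers the 4-week rate, which is certainly CO-validated. And the rule is unlimited in three places, although the authors did write a time-limited version for week 4, so the literal reading is not excluded. An analysis plan could choose a derivation, but the protocol's endpoint list would still name something that is not measured.

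**Conclusion.** The point holds as an inconsistency of moderate weight. The 24-week sustained abstinence endpoint cannot be delivered as CO-validated, because no CO reading is requested or scheduled then. The missing-validation rule lacks a time limit. Read literally it gives 0% in both arms at 24 weeks and extends to 24-week point prevalence, while the more natural reading is self-report with loss to follow-up counted as non-abstinence.

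The reach is limited to secondary outcomes at 24 weeks. The primary endpoint, the 4-week endpoint and the 24-to-52-week endpoint all have the CO reading they need, and the sample size does not depend on the 24-week rate. This is therefore not a must-fix.

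The contradiction rests on the protocol's wording alone and on no assumption. Only the non-zero 24-week counts above depend on one, namely 25% relapse in both arms, and the conclusion does not use them.

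**What to change.** Change the wording in the synopsis and in sections 6.2 and 6.4; sections 4.4 and 4.8 can stay as they are.

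- In the section 6.2 endpoint list, keep CO validation for the 4-week rate and list 24-week sustained abstinence separately as self-reported.
- State that 24-week 7-day point prevalence is also self-reported.
- In all three places, limit the rule on missing biochemical validation to weeks 4 and 52. At 24 weeks keep only the part that counts participants lost to follow-up as non-abstainers.
- Wherever 24-week rates appear beside the 4- and 52-week rates, mark them as unvalidated.

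The cost is a few lines of text, and a 24-week endpoint openly described as weaker than it now sounds. Adding a CO reading at 24 weeks would also reconcile the sections, but it needs an extra collection that is not currently planned; the wording change does not.

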Study Centre(s)	
 1. Tobacco Dependence Research Unit, Wolfson Institute of Preventive Medicine, QMUL 2. East Sussex Stop Smoking Service (Quit 51) 3. Leicester Stop Smoking Service
Objectives	
Primary: To determine the 12-month sustained biochemically validated abstinence rates in smokers using EC compared to smokers using standard NRT.
 
Secondary: Abstinence rates at 4 weeks and 6 months, CO validated sustained abstinence rates between 6 and 12 months, effects of the two treatments on smoking reduction in participants who did not achieve full abstinence, changes in urges to smoke and other tobacco withdrawal symptoms at 1 and 4 weeks, ratings of the two treatment approaches by patients, rates of adverse reactions associated with the use of EC and NRT, cost-effectiveness of EC compared to NRT.

Number of Subjects/Patients	886 randomised participants
Main Inclusion/Exclusion Criteria	
Inclusion criteria: 18 years and older, current smoker accessing a stop smoking service, able to read/write/understand English.
 
Exclusion criteria: Pregnant or breastfeeding, strong preference to use or not to use NRT or EC in the quit attempt, currently using NRT or EC, already enrolled in interventional research.

Statistical Methodology and Analysis	
Abstinence rates and rates of those sustaining a 50% or greater reduction in baseline cigarette consumption and CO levels will be compared between the study arms using a Pearson Chi-squared test with logistic regression. Frequency of adverse reactions will be compared between arms. Time to relapse will be analysed using a Cox analysis. If no significant difference in abstinence rates is detected between the study arms then a non-inferiority analysis will be undertaken. Participants lost to follow-up or not providing biochemical validation will be included as non-abstainers.

GLOSSARY

AE	Adverse event
AR	Adverse reaction
CO	Carbon monoxide
CPD	Cigarettes per day
DMEC	Data Monitoring and Ethics Committee
EC	Electronic cigarette
EQ5D	European Quality of Life -5 Dimensions
FTND	Fagerstrom Test of Nicotine Dependence
JMRO	Joint Management Research Office
LOR	Letter of recommendation
MPSS	Mood and physical symptoms scale
NRT	Nicotine replacement therapy
QA	Quality assurance
QC	Quality control
RCT	Randomised controlled trial
SAE	Serious adverse event
SAR	Serious adverse reaction
SSC	Study Steering Committee
SSS	Stop Smoking Service

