2.1 Trial Objectives

Primary Objective - To determine the 12-month sustained, biochemically validated abstinence rates in smokers using EC compared to smokers using standard NRT.

Secondary Objectives -

1. Abstinence rates at 4 weeks and 6 months.
2. Abstinence rates between 6 and 12 months
3. Effects of the two treatments on smoking reduction in participants who did not achieve full abstinence.

4. changes in urges to smoke and other tobacco withdrawal symptoms at 1 and 4 weeks.
5. Ratings of the two treatment approaches by patients.
6. Rates of adverse reactions associated with the use of EC compared to standard NRT.
7. Cost-effectiveness of EC compared to standard NRT.

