6.3 Sample Size

From extensive past experience, the 12-month validated abstinence rate (Primary outcome) associated with UC in our setting is 14% [51]. Our projection of a feasible rate with the EC is based on our work and two published studies. Our recent work [52] suggests that EC delivers nicotine quickly, with T_{max} occurring within 5 minutes. This is similar to nicotine nasal spray. In a comparative study of the nasal spray + patch versus patch alone, 1-year abstinence rates were 27% vs. 11%, RR= 2.45 [53]. More relevant, in a recent cohort study a second generation EC achieved 36% CO validated abstinence at 6-months [54]. Assuming 25% relapse between 6 and 12 months [55], this would translate to a 1-year rate of 27%. Relative to our assumed UC rate, this would give RR = 1.9. However, in deciding an appropriate sample size for this study we have been more conservative. We wish to detect a RR of 1.7 (EC rate = 24%) with 0.95 power, but also have reasonable power (say, 0.75) if the RR should be as low as 1.5 (EC rate = 21%). This latter figure would still represent a clinically significant difference. To achieve these levels of power (2-sided, alpha = 0.05, continuity correction), a total of 886 participants (443 in each group) are required.

If we find no significant difference in abstinence rates between the study arms then we will undertake a non-inferiority analysis. Our sample size of 886 will provide 90% power to exclude a difference in favour of the standard group of more than 5%.

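### The smoking-reduction endpoint is defined among non-abstainers, a subset formed after randomisation, while the analysis text carries no such restriction and does not say whether abstainers count as reducers

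*Protocol*

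**What the plan says.** Three places restrict reduction to people who go on smoking. The objectives row of the Protocol synopsis lists "effects of the two treatments on smoking reduction in participants who did not achieve full abstinence". Section 2.1 repeats this as secondary objective 3. Section 6.2 gives the endpoint as "Smoking reduction in participants who did not achieve full abstinence".

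Two places describe the comparison, and neither repeats the restriction. Section 6.4 compares the arms on the proportions of participants "sustaining a 50% or greater reduction in baseline cigarette consumption and CO levels at 52 weeks, using Chi-squared test/logistic regression". The statistics row of the synopsis likewise has the rates of sustained reduction compared between arms, with no subset named.

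Section 6.4 adds: "An intention to treat analysis will be used with participants lost to follow-up or not providing biochemical validation included as non-abstainers". This settles how missing outcomes count for abstinence. It does not say who is in the denominator for reduction, whether an abstainer is also a reducer, or how a lost participant counts for reduction.

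**The concern.** Non-abstinence at 52 weeks is the complement of the primary endpoint and is known only after treatment has acted. If EC works as planned, some people who would have stayed in the non-abstainer group on NRT leave it on EC. The two non-abstainer groups then differ in size and possibly in make-up, and a chi-squared test or logistic regression between them is no longer protected by randomisation.

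The direction matters. If the people whom EC moves to abstinence are those who would otherwise have cut down, the EC non-abstainers lose their likeliest reducers. EC then looks worse on reduction with nobody having done worse. The protocol's two wordings leave open whether the analysis falls into this, so one data set could be reported in several ways.

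**Working it through.** **The plan's own figures.** The protocol gives no figure for the reduction endpoint. Its abstinence rates come from section 6.3, where the design case is stated as "We wish to detect a RR of 1.7 (EC rate = 24%) with 0.95 power". Using the usual two-proportion formula with continuity correction, n_cc = (n/4)·[1 + √(1 + 4/(n·d))]², two-sided alpha 0.05:
- 14% v 21%, power 0.75: n = 409, so n_cc = 437 per arm (874 in total).
- 14% v 23.8% (RR exactly 1.7), power 0.95: n = 412, so n_cc = 432 per arm (864 in total).
- At 443 per arm, corrected power is 0.757 and 0.955 respectively.

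The 886 is therefore adequate and is not in question.

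**Size of the subsets.** UC: 443 × 0.86 ≈ 381 non-abstainers. EC: 443 × 0.76 ≈ 337.

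**Illustration.** Assumption, not in the protocol: 30% of all UC participants reduce by at least 50% without quitting. EC adds 10 points of abstinence and has no other effect. What varies is the share of those extra quitters who would have been reducers on NRT.

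| Share who would have reduced | EC reduced | Non-abstainers only, UC v EC | All randomised, abstainers not counted | All randomised, abstainers counted |
|---|---|---|---|---|
| All | 30 − 10 = 20% | 30/86 = 34.9% v 20/76 = 26.3% | 30% v 20% | 44% v 44% |
| Half | 30 − 5 = 25% | 34.9% v 25/76 = 32.9% | 30% v 25% | 44% v 49% |
| 34.9%, as other UC non-abstainers | 30 − 3.5 = 26.5% | 34.9% v 26.5/76 = 34.9% | 30% v 26.5% | 44% v 50.5% |

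The chi-squared test on the subset counts gives p = 0.014 in the first row (133/381 v 89/337; 0.017 with continuity correction) and p = 0.58 in the second.

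The third row shows that an all-randomised denominator is not enough by itself. If abstainers are left out of the numerator, EC loses 3.5 points even where the subset comparison is unbiased, because each reducer who quits stops counting.

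**Range.** Let r be the probability of reduction among people who quit on neither treatment (the same in both arms), and m the probability that someone who quits only on EC would have reduced on NRT. Among non-abstainers, the EC rate is r and the UC rate is (0.76·r + 0.10·m)/0.86. The difference, EC minus UC, is −(0.10/0.86)·(m − r). It is zero when m = r, goes against EC when m > r, and favours EC when m < r. Over the assumed ranges r = 15–35% and m = 50–100%, the subset risk ratio runs from 0.60 to 0.95 (0.68 to 0.97 if EC abstinence is 21%). With r = 25% and m = 50% it is 25.0%/27.9% = 0.90. Over the same ranges at 24% EC abstinence, abstinent-or-reduced in all randomised gives 1.00 to 1.16.

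**The case against.** A reader might infer that the protocol compares reduction only among people who did not quit. It does not say so. The restriction stands in the objective and endpoint wording; both descriptions of the comparison omit it, and section 6.4 states intention to treat. On one reading section 6.4 is already close to sound: an abstainer has cut cigarettes to almost nothing and will usually meet the CO criterion, so the proportion with at least 50% reduction in all randomised would be roughly abstinent-or-reduced. That reading is available, but it is not stated and it contradicts sections 2.1 and 6.2. Nor does every abstainer qualify automatically: with a cut-off of 8 ppm, someone with a baseline CO below 16 ppm can be validated as abstinent without halving CO. Section 1.2 also describes an earlier cohort with reducers and an additional share of abstainers as separate groups, which points to the reading that leaves abstainers out.

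It can be said that the choice belongs in an SAP, which is not shown. Detail does. The population of this endpoint, however, is written into the protocol three times, and an SAP that followed it would test a non-randomised subset.

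It is also fair that the bias is not certain. It needs m > r, a real EC effect on continuing smokers could offset it, and in the half case the 2.0-point gap is small against a standard error of about 3.5 points. Finally, a composite answers a different question from objective 3 and overlaps with the primary endpoint. That cost is real and is met in the fix.

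**Conclusion.** The point holds as a conflict between endpoint and analysis, with a real risk of bias under two of the three possible readings. The endpoint is defined in a subset that treatment is expected to change. The analysis text neither adopts that subset nor says what replaces it. Testing among non-abstainers is not a randomised comparison; testing in all randomised with abstainers left out of the numerator counts quitting against EC. Only the reading in which abstainers count is free of this, and it does not match the stated endpoint.

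The size is conditional. The 8.6-point gap (34.9% v 26.3%) needs an assumed 30% reduction rate on UC and every extra quitter drawn from would-be reducers. It falls to 2.0 points if half are, and to zero if they reduce at the same 34.9% rate as other UC non-abstainers. A reader might infer that a reversal is to be expected whenever the trial succeeds. The documents do not support that: they fix the abstinence rates but not the reduction rates that drive the sign. One secondary endpoint is affected.

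**What to change.** Align the synopsis, section 2.1, section 6.2 and section 6.4:

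- **Tested endpoint:** CO-validated abstinence, or CO-confirmed reduction of at least 50% from baseline, at 52 weeks, in all 886 randomised. State that abstainers count as successes and that missing participants count as neither. Analyse it in the same way as the primary endpoint.
- **Beside it:** a table of abstinent, reduced and neither by arm, with all randomised as denominator.
- **Descriptive only:** reduction among non-abstainers, without a between-arm test and labelled as a non-randomised comparison.

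No new data are needed. Sections 4.4 and 4.8 already collect smoking status and daily consumption at 52 weeks, request CO from those reporting abstinence or at least 50% reduction, and record both measures at baseline. The cost is a wording change in four places.

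The downside is that the composite overlaps with the primary endpoint and does not isolate reduction in continuing smokers. In the first row of the illustration it shows 44% v 44% and hides a 10-point gain in abstinence. The three-category table is there so that a reader can see this.
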